### **Methods**

#### 1. Study design:

This study employed a single-blind, randomized controlled trial. Two parallel groups with two assessment periods was adopted to evaluate the effects of the intervention. The inclusion criteria were as follows: (1) age 60 to 80 years, (2) diagnosed with hypertension for at least 6 months, (3) self-reported indications of problems with memory or thinking skills. The exclusion criteria were as follows: (1) probable cognitive impairment as assessed by the Montreal Cognitive Assessment (< 24 points); T(sai et al., 2012), (2) significant conditions limiting walking ability (e.g., musculoskeletal problems, visual impairment), (3) already participating in 30 minutes or more of moderate-intensity exercise five times a week, (4) a history of severe cardiovascular disease, and (5) a history of neurologic or psychiatric disorders such as stroke, head injury dementia, Parkinson's disease, and depression.

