## 2. Research tools:

Data collected for this study also included demographic, health-related, and disease-related information in pretest and posttest data collection. The primary outcome was memory performance, which was measured with the Hopkins Verbal Learning Test; the secondary outcomes were subjective cognitive complaints and brain-derived neurotrophic factor. Subjective cognitive complaints were measured with the Cognitive Failures Questionnaire, and brain-derived neurotrophic factor was measured through laboratory analysis of blood samples.

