## **Statistical Analysis Plan**

Data were analyzed using the Statistical Package for the Social Sciences (SPSS) version 25 for Windows (Chicago, IL, USA). Descriptive statistical methods were implemented to characterize the characteristics of the participants and study variables. Independent *t*-tests, chi-square tests, and Fisher's exact test were used to examine the homogeneity between the two groups. Paired *t*-tests were employed to examine the changes in each group between the pretest and 24 weeks in memory, subjective cognitive complaints, and brain-derived neurotrophic factor. The generalized estimating equation was used to evaluate whether memory, subjective cognitive complaints, and brain-derived neurotrophic factor were different between groups at pretest and after 24 weeks. A significance level of 5% was used for between-group comparisons and interaction terms.

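### The between-group GEE works out to an unadjusted difference in mean change; adjusting the 24-week value for the pretest would be more precise, and t-based inference would remove any small-sample excess

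*Combined protocol and SAP*

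**What the plan says.** The Methods section, under Study design, describes a randomised trial: "Two parallel groups with two assessment periods was adopted". Under Research tools the primary outcome is named: "The primary outcome was memory performance, which was measured with the Hopkins Verbal Learning Test". Subjective complaints and brain-derived neurotrophic factor are secondary, and data are collected at pretest and posttest.

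The Statistical Analysis Plan gives one between-group efficacy method for all three outcomes: "The generalized estimating equation was used to evaluate whether memory, subjective cognitive complaints, and brain-derived neurotrophic factor were different between groups". The same sentence applies this to the pretest as well as the 24-week values. It adds: "A significance level of 5% was used for between-group comparisons and interaction terms". The pretest therefore enters as one of the two outcome values, and the treatment effect is read from group and group-by-time terms. The pretest is not named as a covariate.

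The software is named (SPSS version 25). The GEE's mean model, working correlation, variance estimator and reference distribution are not, and no small-sample correction is mentioned. The document gives no sample size, allocation ratio, standard deviation, pretest-posttest correlation or dropout figure.

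**The concern.** Two things are at stake, of different weight.

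- **Precision.** A group-by-time term from two visits takes the pretest off with a fixed coefficient of 1. Unless pretest and posttest are almost perfectly correlated, that over-subtracts and brings pretest noise into the treatment estimate. The price is wider intervals and lower power for the memory outcome and both secondary outcomes, at every sample size.
- **Calibration in small arms.** GEE inference is a large-sample method. A robust variance without correction is slightly too small on average, and a normal reference gives a critical value slightly too low. Both push the error rate above 5%. The plan does not say whether this combination is used, and without a sample size nobody can tell whether it would matter.

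**Working it through.** **Inputs.** From the document: two parallel groups, two assessments, randomisation, a GEE with group and interaction terms, and a 5% level. Assumed, because the document is silent: a two-sided test, equal arms of n, complete data, continuous outcomes with common SD sigma at both visits, and pretest-posttest correlation rho of 0.5 to 0.7. The plan states no figure that could be reproduced first.

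**Step 1: what the interaction estimates.** A model with group, time and group-by-time has four mean parameters for four cell means. With complete data the interaction is (24-week minus pretest mean, intervention) minus (24-week minus pretest mean, control), that is, the difference in mean change.

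**Step 2: variances of the group difference.**
- Change contrast: (2/n) × sigma² × 2(1 − rho)
- 24-week value adjusted for pretest: (2/n) × sigma² × (1 − rho²)
- Ratio: (1 − rho²) / [2(1 − rho)] = (1 + rho)/2

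| Assumed rho | Variance ratio | Standard error ratio | Extra participants needed by change contrast, 2/(1+rho) − 1 |
|---|---|---|---|
| 0.5 | 0.75 | 0.87 | 33% |
| 0.6 | 0.80 | 0.89 | 25% |
| 0.7 | 0.85 | 0.92 | 18% |

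The ratio treats the pretest slope as known. Estimating it multiplies the adjusted variance by about 1 + 1/(2n − 4) for normal data. At 20 per arm that is 1 + 1/36 = 1.028, so 0.80 becomes 0.82. A simulation at 20 per arm and rho 0.6 (20,000 runs) also gave 0.82.

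The direction does not need equal variances. With SDs s1 (pretest) and s2 (posttest), the change variance minus the adjusted variance is (s1² + s2² − 2·rho·s1·s2) − s2²(1 − rho²) = (s1 − rho·s2)², which is never negative.

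**Step 3: the other reading of the GEE.** If the treatment effect is instead the group difference at 24 weeks from the same model, its variance is (2/n) × sigma². The adjusted estimate then has 1 − rho² of it: 0.75, 0.64 and 0.51 at rho 0.5, 0.6 and 0.7. Adjustment gains on either reading.

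**Step 4: error rate if the robust variance is uncorrected.** In this design the uncorrected sandwich variance is (n − 1)/n of the unbiased one. With normal data, equal variances and a normal reference, the true two-sided level is P(|t| > 1.96 × √((n − 1)/n)) on 2n − 2 degrees of freedom.

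| Assumed n per arm | Critical value applied to t | df | True level | Interval width relative to t interval |
|---|---|---|---|---|
| 10 | 1.859 | 18 | 7.9% | 0.885 |
| 20 | 1.910 | 38 | 6.4% | 0.944 |
| 30 | 1.927 | 58 | 5.9% | 0.963 |
| 50 | 1.940 | 98 | 5.5% | 0.978 |
| 100 | 1.950 | 198 | 5.3% | 0.989 |

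Simulated GEE fits with a robust variance (3,000 runs each, Monte Carlo standard error 0.4 points) rejected 6.8% at 15 per arm, where the formula gives 6.9%, and 5.8% at both 30 and 50. These agree with the formula within simulation error.

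With an unbiased variance but still a normal reference, the level would be 5.7% at 20 per arm, 5.5% at 30 and 5.3% at 50. An unbiased variance with a t reference on 2n − 2 degrees of freedom gives 5.0% under these assumptions.

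**The case against.** The strongest reply is that a GEE on a randomised two-arm pretest-posttest design is valid, so preferring baseline adjustment is a matter of efficiency. That is correct, and the point is put here as one of precision, not bias. The gain rests on an assumed correlation and shrinks as rho approaches 1.

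A reader might go further and infer that the plan's 5% level is exceeded and its intervals too narrow at any modest sample size. The document does not support that. It names neither the variance estimator nor the reference distribution, and silence does not show that an uncorrected robust variance was used. Without a sample size the excess cannot be placed on the range above, and from about 50 per arm it is roughly half a point or less. Nor are the levels in the working this trial's error rates: they are exact only for complete, normal, equal-variance, equal-arm data.

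A reader might also infer that GEE offers nothing here. That overstates it. GEE can use a participant with only one visit if data are missing completely at random, and its robust variance does not depend on equal variances or normality. A complete-case linear model drops anyone lacking either visit. This part of the objection stands, and is why the fix includes a likelihood-based alternative.

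Finally, the plan is written in the past tense. If the analysis is done, replacing the primary model would be a post hoc change. That also stands and limits how a new model should be presented.

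**Conclusion.** The concern holds as a point about precision. For two arms and two visits with complete data, the interaction the plan tests is an unadjusted difference in mean change. Adjusting for the pretest would cut its variance to about 0.75 to 0.85 of that value at assumed correlations of 0.5 to 0.7 with equal variances; the slope-estimation penalty is under 3% from 20 per arm. Its direction holds at any correlation and for unequal variances, apart from that penalty.

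The small-sample point is secondary and conditional. It applies only if the GEE uses an uncorrected robust variance with a normal reference, and it is of practical size mainly at about 20 per arm or fewer. What can be said firmly is that the plan leaves these options unstated, so the GEE cannot be reproduced as written and its calibration cannot be judged.

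**What to change.** - **Primary analysis, each outcome:** a linear model of the 24-week value on group and pretest value, reporting the adjusted group difference with a t-based 95% confidence interval.
- **If either visit may be missing:** a likelihood mixed model of both visits with a common pretest mean across arms and Satterthwaite degrees of freedom. It keeps participants with one visit and retains the baseline adjustment.
- **GEE:** report as a sensitivity analysis, stating the mean model, working correlation, variance estimator and reference distribution, with a small-sample corrected variance and a t reference.
- **Sample size:** state the number randomised per arm, so that a reader can judge the small-sample issue.
- **If the data are already analysed:** label the adjusted model as an added analysis and show it beside the planned GEE, not in place of it.

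The cost is wording in the Statistical Analysis Plan and one model specification. No new data or participants are needed, and the linear model runs in the named software. The downsides are that a complete-case linear model loses participants missing a visit, which the mixed model avoids, and that p-values from an uncorrected GEE, if that is what was run, may look slightly more favourable than corrected ones.
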